### ***2.2 Study objective***

We hypothesize that surgical patients with IAPI can be identified. The aims of this study are to develop and validate a reliable and simple surgical patient IAPI risk prediction model by a prospective multicenter cohort data based on the combination of the indicators and practical experience of the most used assessment tools.

### ***2.3 Setting***

The patients will be recruited from the operating rooms of nine tertiary hospitals in China: Affiliated Hospital of Guangdong Medical University (Guangdong), First Affiliated Hospital of Sun Yat-sen University (Guangdong), Foshan First People's Hospital (Guangdong), First Affiliated Hospital of Zhengzhou University (Henan), and The First Affiliated Hospital of Nanchang University (Jiangxi).

## ***2.4 Participants and Eligibility criteria***

Participants who meet the inclusion criteria: all patients who underwent surgery procedure at the participating setting after the study registration.

Exclusion criteria: Patients who have already been diagnosed with pressure injury (stage II and above) before undergoing surgery procedure. Patients/relatives/guardians understand the refusal of data to be used for clinically relevant research. Investigators believe that certain patient conditions may affect the efficacy and safety assessment of this study.

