### **Methods:**

We will use a pre-set observational assessment scale that consists of 24 indicators to construct the predictive model in this study. In addition to these pre-set indicators, the researchers will also collect other relevant indicators that they believe may contribute to the predictive model. Primary outcome was incidence of IAPI of any stage at 7 days from operating room admission. Secondary outcomes were in-hospital mortality (follow-up endpoint is 3 months after surgical procedure), surgical complication, and hospitalization costs. The prospective cohort study dataset is divided randomly into two

subsets: a training group (80% of the data) and an internal validation group (20% of the data). The training group is used for model development, while the internal validation group remains untouched until later stages. In model development, researchers can explore different variables and test various machine learning algorithms, such as logistic regression, artificial neural network (ANN), XGBoost, support vector machine (SVM), k-nearest neighbors (k-NN), naive Bayes, gradient boosting machines (GBM), AdaBoost, Gaussian mixture model (GMM), and support vector regression (SVR). They can train and optimize these models using the training dataset. After training the models on the training dataset, researchers can evaluate their performance using appropriate evaluation metrics (e.g., accuracy, precision, recall, F1-score, area under the receiver operating characteristics curve). Based on the evaluation results, we refine the model by tweaking hyperparameters, feature selection, or employing techniques like cross-validation or grid search. This iterative process aims to find the best-performing model configuration. Once the model is optimized using the training dataset, it is then evaluated on the internal validation dataset. This evaluation serves as an unbiased assessment of the model's performance on unseen data, providing an estimate of its ability to generalize. Based on the performance on the internal validation dataset, to choose the best-performing model as the final predictive model.

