## ***2.5 Variables***

### ***2.5.1 Outcome measure***

The primary outcome of this study is IAPI in patients who underwent surgery procedure. IAPI is a localized skin injury caused by the prolonged action of pressure, friction, and (or) shear forces during surgery, most occurring within 1-3 days postoperatively, and also within 6 days postoperatively. The severity of pressure injuries is classified using the National Pressure Ulcer Advisory Panel Pressure Injury Staging System:

- Stage 1 Pressure Injury: The skin is intact with erythema that does not change white in local acupressure.***

Intact skin with a localized area of nonblanchable erythema, which may appear differently in darkly pigmented skin. Presence of blanchable erythema or changes in sensation, temperature, or firmness may precede visual changes. Color changes do not include purple or maroon discoloration; these may indicate deep tissue pressure injury.

- ***Stage 2 Pressure Injury: Partial-thickness skin loss with exposed dermis.***

Partial-thickness loss of skin with exposed dermis. The wound bed is viable, pink or red, moist, and may also present as an intact or ruptured serum-filled blister. Adipose (fat) is not visible and deeper tissue is not visible. Granulation tissue, slough and eschar, are not present. These injuries commonly result from adverse microclimate and shear in the skin over the pelvis and shear in the heel.

- ***Stage 3 Pressure Injury: Full-Thickness Skin Loss***

Full-thickness skin loss, in which adipose (fat) is visible in the ulcer and granulation tissue and epibole (rolled wound edges), is often present. Slough and/or eschar may be visible. The depth of tissue damage varies by anatomical location; areas of significant adiposity can develop deep wounds. Undermining and tunneling may occur. Fascia, muscle, tendon, ligament, cartilage, or bone is not exposed. If slough or eschar obscures the extent of tissue loss, this is an unstageable pressure injury.

- ***Stage 4 Pressure Injury: Full-Thickness Skin and Tissue Loss***

Full-thickness skin and tissue loss with exposed or directly palpable fascia, muscle, tendon, ligament, cartilage, or bone in the ulcer. Slough and/or eschar may be visible. Epibole (rolled edges), undermining, and/or tunneling often occur. Depth varies by anatomical location. If slough or eschar obscures the extent of tissue loss, this is an unstageable pressure injury.

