- ***Unstageable Full-Thickness Pressure Injury: Obscured Full-Thickness Skin and Tissue Loss***

Full-thickness skin and tissue loss in which the extent of tissue damage within the

ulcer cannot be confirmed because it is obscured by slough or eschar. If slough or eschar is removed, a Stage 3 or Stage 4 pressure injury will be revealed. Stable eschar (ie, dry, adherent, intact without erythema or fluctuance) on ischemic limb or heels should not be softened or removed.

- ***Deep Tissue Pressure Injury: Persistent Nonblanchable Deep Red, Maroon or Purple Discoloration***

Intact or nonintact skin with localized area of persistent nonblanchable deep red, maroon, purple discoloration, or epidermal separation revealing a dark wound bed or blood-filled blister. Pain and temperature change often precede skin color changes. Discoloration may appear differently in darkly pigmented skin. This injury results from intense and/or prolonged pressure and shear forces at the bone-muscle interface. The wound may evolve rapidly to reveal the actual extent of tissue injury or may resolve without tissue loss. If necrotic tissue, subcutaneous tissue, granulation tissue, fascia, muscle, or other underlying structures are visible, this indicates a full-thickness pressure injury (unstageable, Stage 3, or Stage 4). Do not use DTPI to describe vascular, traumatic, neuropathic, or dermatologic conditions.

- ***Medical Device–Related Pressure Injury***

Medical device–related pressure injuries result from the use of devices designed and applied for diagnostic or therapeutic purposes. The resultant pressure injury generally conforms to the pattern or shape of the device. The injury should be staged using the staging system.

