12. Tissue Malnutrition
Multiple organ failure/terminal cachexia
Single organ failure e.g., cardiac, renal, respiratory
Peripheral vascular disease
Anaemia (Hb < 80 g/L)
Smoking

13. Continence
Complete/catheterised
Incontinent urine
Incontinent faeces
Doubly incontinent (urine & faeces)
14. Mobility
Fully mobile
Restless/fidgety
Apathetic (sedated/depressed/reluctant to move)
Restricted (restricted by severe pain or disease)
Bedbound (unconscious/unable to change position/traction)
Chair bound (unable to leave chair without assistance)
15. Major surgery
On table > 6 hours
Orthopaedic/ below waist/spinal (up to 48 hours post op)
On table > 2 hours (up to 48 hours post op)
16. Neurological deficit
Motor/sensory
Diabetes
Paraplegia
Cardiovascular and cerebrovascular diseases/ multiple sclerosis (MS)/ cerebrovascular accident (CVA)
17. Medication
Long term/high dose steroid
Cytotoxic
Anti-inflammatory
Norton scale
18. Physical condition
Very bad
Poor
Fair
Good
19. Mental condition
Stupor
Confused
Apathetic
Alert
20. Activity
Bed
Chairbound
Walks with help
Ambulant
21. Mobility

Mobility	
Slightly limited	
Very limited	
Immobile	
22. Incontinent	
Doubly	
Usually (urine)	
Occasionally	
No	
Cubbin & Jackson scale	
23. Age	
<40	
40-55	
56-70	
>70	
24. Weight	
Average weight	
Obese	
Cachectic	
Any of above and oedema	
25. General skin condition	
Intact	
Red skin	
Grazed/excoriated/skin	
Necrosis/exuding	
26. Mental condition	
Awake and alert	
Agitated/restless/confused	
Apathetic/sedated but responsive	
Coma/unresponsive/unpurposeful movements	
27. Mobility	
Fully ambulant	
Walks with slight help	
Very limited/chairbound	
Immobile/bedrest	
28. Haemodynamic status	
Stable without inotropic support	
Stable with inotropic support	
Unstable with inotropic support	
Critical with inotropic support	
29. Respiration	
Spontaneous	
Continuous positive airway pressure (CPAP)/T-piece	

Mechanical ventilation
Breathless at rest/on exertion
30. Nutrition
Full diet + fluids
Light diet/oral fluids/enteral
Parenteral feeding
Clear IV fluids only
31. Incontinence
None/anuric/catheterised
Urine
Faeces
Urine + faeces
32. Hygiene
Competent in maintaining own hygiene
Maintaining own hygiene with slight help
Requires much assistance
Fully dependent
Munro scale
Preoperative Risk Factor Score

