## 51. Other variables (at the discretion of the nurse/doctor)

### 3.3 Schedule of Events

The events schedule comprised three sequential stages: recruitment and screening, baseline assessment, and outcome follow-up. The primary endpoint of this study is to evaluate the clinical outcomes three months post-surgery, its follow-ups should be office visits, but telephone contact will be allowed. Data collected during all follow-up visits will include IAPI, SSI, surgical complication, death. Original source documents must be submitted for any clinical events (death, IAPI, SSI, surgical complication, within 3 months).

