**Table 2 Schedule of Events in the observational cohort for this study.**

	Recruitment & screening	Baseline assessments	Follow up						
			0.5 hours	2 hours	24 hours	48 hours	72 hours	7 days	3 months
Informed consent 	X	X							
Inclusion/exclusion criteria	X	X							
Demography/ Surgical procedures	X	X							
Potential predictor variables		X							
IAPI			X	X	X	X	X	X	X
SSI						X	X	X	X
Surgical complication 			X	X	X	X	X	X	X
Death			X	X	X	X	X	X	X

Abbreviation: IAPI: intraoperatively acquired pressure injure, SSI: surgical site infections.

 The informed consent should be signed prior to the surgical procedures, but it can be signed after the surgical procedures in the urgent situation.

 The surgical complications in patients during the same hospitalization will also be observed, as defined by the Clavien-Dindo classification.

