## 4. Data Analysis

### 4.1 Sample size

The primary outcome of this study is IAPI in patients who underwent surgery procedure.

The fixed position of surgical patients in the surgical procedure, and the occurrence of IAPI risk is time-dependent, which it is positively correlated with the advancement of time and the occurrence of IAPI events in surgical patients. For time-to-event outcomes, ensure the sample size is enough to: Estimate the overall outcome proportion with sufficient precision at one or more key time-points in follow-up; Target a shrinkage factor of 0.9; Target small optimism of 0.05 in the apparent  $R^2_{\text{Nagelkerke}}$ . The formula provided by Riley et al. is as follows:

Time-event-outcome, the sample size (number of participants, n) required to achieve the expected uniform contraction coefficient S can be expressed as:

$$n = \frac{P}{(S-1)\ln\left(1 - \frac{R_{cs}^2}{S}\right)}$$

To calculate the sample size, to ensure that the expected optimistic value of  $R^2$  (i.e.,  $R_{cs}^2/\max(R_{cs}^2)$ ) has a smaller expected optimism. For time-event-outcome, the first step is to calculate the contraction coefficient corresponding to the expected optimistic value in  $R^2_{\text{Nagelkerke}}$ :

$$S = \frac{R_{cs}^2}{R_{cs}^2 + \delta\max(R_{cs}^2)}$$

The recent randomized controlled trial results showed an incidence of IAPI (stage I and above) of 13.9%, assuming 0.05 acceptable difference in apparent & adjusted

R-squared. The study used the R4.1.2 software (pmsampsize package) to estimate the minimum sample size required to develop the new model. Minimum sample size required for new model development is 4115, with 572 events (assuming an outcome prevalence = 0.139) and an Events per Predictor Parameter (EPP) is 23.83. In addition, according to the pre-model design requirements, the total sample was divided into 80% samples for the development of the new model and 20% samples for the validation of the model. This means that a total of 5144 cases are required. Considering a possible 10% loss of follow-up, the minimum sample size required for the prediction model was 5658 cases.

```
NB: Assuming 0.05 acceptable difference in apparent & adjusted R-squared
NB: Assuming 0.05 margin of error in estimation of intercept
NB: Events per Predictor Parameter (EPP) assumes prevalence = 0.139
```

	Samp_size	Shrinkage	Parameter	CS_Rsq	Max_Rsq	Nag_Rsq

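### A stage I pressure injury present before surgery can be counted as a primary-outcome event, and the primary endpoint is placed at both 7 days and three months

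*Combined protocol and SAP*

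**What the plan says.** **Who may enter.** Section 2.4 admits all surgical patients at the participating hospitals. Among prior pressure injuries it excludes only "Patients who have already been diagnosed with pressure injury (stage II and above) before undergoing surgery procedure". Stage I is not excluded.

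**What counts as an event.** The abstract (Methods) states: "Primary outcome was incidence of IAPI of any stage at 7 days from operating room admission". Section 2.5.1 describes IAPI as injury "caused by the prolonged action of pressure, friction, and (or) shear forces during surgery" and then gives a staging list that begins with stage 1. Section 4.1 plans on trial results that "showed an incidence of IAPI (stage I and above) of 13.9"%.

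**How it is recorded.** In Table 2 the IAPI row starts at 0.5 hours after surgery and runs to 3 months. The baseline column has no entry for existing pressure injury. The skin items among the predictors in Table 1 (items 9 and 25, the latter with a category for red skin) carry neither a body site nor a pressure-injury stage.

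**When.** Against the abstract's 7 days, section 3.3 says: "The primary endpoint of this study is to evaluate the clinical outcomes three months post-surgery", and has IAPI collected at every follow-up visit. Section 2.6 and Table 2 list a day-7 visit; section 3.2 goes from 72 hours straight to three months. The abstract counts from operating room admission, section 2.6 from surgery.

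**The concern.** Every model is trained and tested on this outcome and compared with the five existing scales on it (sections 4.2.1 and 4.2.2). It is also the exposure in the mortality analysis (section 4.2.3).

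The eligibility rule lets stage I in and the outcome rule counts stage I. Nothing in between says what to do with a lesion that was there before the operation. Three consequences are possible: incidence is overstated; assessors at different hospitals classify the same lesion differently; and a baseline skin item, if selected, predicts a lesion that it already describes. If lesion sites are not recorded before surgery, they may not be recoverable afterwards.

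On timing, 7 days and three months give different event sets. The longer one could take in injuries acquired on the ward or at home well after surgery. While both stand as primary, the choice could be made after the data are seen.

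**Working it through.** **1. The passages side by side**

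| Question | Place | Answer |
|---|---|---|
| Is prior stage I excluded? | 2.4 | No |
| Is stage I an event? | Abstract; 2.5.1; 4.1 | Yes |
| Must the injury be new? | 2.5.1 | Implied by the cause, but no test given |
| Is lesion site recorded before surgery? | Tables 1 and 2 | Not in the documents |
| Is there a new-site or worsening rule? | Whole plan | None found |
| Is prior deep tissue injury excluded? | 2.4; 2.5.1 | Unclear: it has no stage number |

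Unstageable injury is not in doubt. Section 2.5.1 says that it conceals a stage 3 or 4 lesion, so the exclusion already covers it.

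**2. The plan's own figures**

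With P = 24, S = 0.9 and Cox-Snell R² = 0.051 (section 4.1), n = 24 / [(0.9 − 1) × ln(1 − 0.051/0.9)] = 4114.1, rounded up to 4115. Events: 4115 × 0.139 = 572. Events per parameter: 4115 × 0.139 / 24 = 23.83. Total: 4115 / 0.8 = 5143.75, so 5144; 5144 × 1.1 = 5658.4, stated as 5658. All agree with the plan. With R² held at 0.051 this formula does not contain the incidence, so a new-lesion rule leaves 4115 unchanged.

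**3. Illustrative size of the misclassification**

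Inputs: true incidence 13.9% (section 4.1); prevalence b of stage I injury at entry, assumed 1%, 3% or 5% because the documents give none; share k of those lesions that persist and are counted, assumed 1, 0.5 or 0.25. I also assume that patients with a carried-over lesion develop a true new injury at the same 13.9%.

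Let c = b × k.

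- Apparent incidence = c + (1 − c) × 0.139.
- False events are carried-over lesions in patients with no true new injury: c × (1 − 0.139) = 0.861c.
- False share of counted events = 0.861c / apparent incidence.

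For b = 3% and k = 1: apparent incidence = 0.03 + 0.97 × 0.139 = 0.1648; false events = 0.861 × 0.03 = 0.0258; share = 0.0258 / 0.1648 = 15.7%.

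| k | Apparent incidence at b = 1%, 3%, 5% | False share of events at b = 1%, 3%, 5% |
|---|---|---|
| 1 | 14.8%, 16.5%, 18.2% | 5.8%, 15.7%, 23.6% |
| 0.5 | 14.3%, 15.2%, 16.1% | 3.0%, 8.5%, 13.4% |
| 0.25 | 14.1%, 14.5%, 15.0% | 1.5%, 4.4%, 7.2% |
| 0 | 13.9% throughout | 0 |

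**4. Patients lost if any prior injury were excluded**

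5658 × 0.01, 0.03 and 0.05 = 57, 170 and 283.

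**The case against.** **The definition already rules out old lesions.** Section 2.5.1 ties IAPI to forces acting during surgery, and the word acquired says the same. This stands as to the concept: it would be wrong to infer that the plan means to count prior lesions. But the cause of an area of erythema seen at 0.5 hours cannot be judged without knowing whether that site was clear beforehand. The planned training (3.2, 3.6), source documents for IAPI (3.3) and monitoring (3.6) can only enforce a rule that exists.

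**Table 2 is right to have no IAPI mark at baseline.** Agreed. A lesion seen before surgery is not IAPI, and such a mark would mislabel it. What is missing is a separate record of existing injury.

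**Section 3.3 is a labelling slip.** Probably so. It speaks of clinical outcomes, the abstract gives three months for mortality, section 4.2 plans 90-day mortality, and sections 2.5.1 and 4.1 name IAPI as primary. Section 2.5.1 places onset mostly in days 1 to 3 and otherwise within 6 days, which suits a 7-day window. Even so, the sentence as written names a primary endpoint that conflicts with the abstract.

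**The two clock origins do not matter.** No effect on event counts has been shown. For an operation in the Table 1 class "On table > 6 hours" the origins differ by more than 6 hours, but no passage sets a closing hour for day 7. This is a matter of wording.

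**The form may handle it.** The electronic form is not in the documents and may hold a site field. That limits what can be said about data capture, but it does not supply the missing rule in the protocol.

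**Conclusion.** The point holds on the text. The stated eligibility and outcome rules together allow a stage I lesion present before surgery to be counted as an event, and the status of prior deep tissue injury is unclear. The primary endpoint also has two stated times, and section 3.2 omits the day-7 visit. This should be corrected, because it concerns what an event is.

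The size is not known. With every baseline stage I lesion counted, false events are about 6%, 16% or 24% of the total at assumed prevalences of 1%, 3% or 5%; the share shrinks with k and is zero if assessors discount such lesions. The case for a change does not depend on these figures.

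A reader might infer more, without support:

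- That the AUC will be biased in a known direction. It depends on whether baseline lesions share the model's predictors and whether a skin item is selected.
- That the sample size is wrong. It reproduces, and criterion 1 does not use the incidence.
- That every carried-over lesion is a false event. Under the assumptions above, 13.9% of those patients would be true events anyway.
- That three months is the real window for IAPI. The rest of the plan points to 7 days.

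**What to change.** **(a) Case definition.** Choose one:

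- Add a pre-operative record of pressure injury, by site and category and labelled as pre-existing, to the baseline column of Table 2. Record lesion site at each follow-up. Count as IAPI only a lesion at a site that was clear at baseline. Flag any worsening of a baseline lesion and handle it by a rule stated in advance, for example a sensitivity analysis. Automatic counting would be unsafe, since section 2.5.1 says of deep tissue injury: "The wound may evolve rapidly to reveal the actual extent of tissue injury or may resolve without tissue loss".
- Or extend the exclusion in section 2.4 to any pre-existing pressure injury.

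In either case state how deep tissue injury present before surgery is treated, and put the rule into the planned training.

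**(b) Timing.** Reconcile the abstract, sections 2.6, 3.2 and 3.3, and Table 2 on one primary IAPI window and one time origin. Seven days agrees with the abstract and with the onset described in section 2.5.1. Correct the primary-endpoint wording in section 3.3, restore day 7 in section 3.2, and report pressure injury at three months descriptively.

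**Cost.** Protocol wording, one or two extra form fields and slightly fewer events. If any prior injury is excluded instead, the cost is about 57 to 283 of 5,658 patients at the assumed 1% to 5%. Neither option separates ward-acquired lesions within 7 days from intraoperative ones; state this as a limitation.

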### **Design:**

A prospective, multicenter, cohort study.

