### **Participants and setting:**

All patients who underwent surgery procedure from operating room of more than 5 tertiary hospitals in China.

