## **2. Methods**

### ***2.1 Study Design***

The proposed study design is a prospective, multicenter, cohort study, which aims to calculate the risk factors that influence the incidence of IAPI. This design allows researchers to observe the natural history of IAPI, and to identify potential risk factors and interventions that may affect the incidence of IAPI.

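### An exclusion on investigator judgement refers to an efficacy and safety assessment that this observational cohort does not have, and leaves sites free to depart from the all-patients population without record.

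*Combined protocol and SAP*

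**What the plan says.** Section 2.4 (Participants and Eligibility criteria) sets the inclusion rule as "all patients who underwent surgery procedure at the participating setting after the study registration". The abstract describes the same population: "All patients who underwent surgery procedure from operating room of more than 5 tertiary hospitals in China". Section 2.4 then gives three exclusions: an existing pressure injury of stage II or above, refusal of data use, and the clause at issue, "Investigators believe that certain patient conditions may affect the efficacy and safety assessment of this study". That clause names no condition, threshold or decision procedure.

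The design is given as "A prospective, multicenter, cohort study". Section 2.1 says "This design allows researchers to observe the natural history of IAPI", and the objective in section 2.2 is to "develop and validate a reliable and simple surgical patient IAPI risk prediction model".

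Table 1 lists the candidate predictors. Several of their levels describe severe illness or dependence: "Multiple organ failure/terminal cachexia" (Waterlow item 12), the worst haemodynamic level (Cubbin & Jackson item 28), full immobility (Munro item 37) and the highest ASA level (Munro item 39).

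Section 3.6 has the data system monitor adherence to the eligibility criteria, and has the study monitor review screening records. Section 4.2.1 splits the enrolled cohort at random, 80% for training and 20% for internal validation.

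**The concern.** The clause reads as if taken from a trial of a treatment. With no study treatment or comparator, a site has no standard for deciding which conditions it covers. Whatever a site decides is within the protocol, so two sites can follow the rule faithfully and still enrol different kinds of patient.

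For a prediction model, the enrolled case mix is the population to which the score applies. If the excluded patients include high-risk ones, the severe levels of some predictors become sparse, the observed incidence and discrimination shift, and the score goes untested in part of its intended population. The planned comparison with the five existing scales (section 4.2.2) would run on the same narrowed group.

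**Working it through.** **1. Is there a referent for the clause?** Sections 2.1 and 2.2 give an observational design and a prediction objective. Section 2.5 lists IAPI, mortality, surgical site infection, complications, length of stay and costs as outcomes. None is an efficacy endpoint or a safety evaluation of an intervention. The clause therefore points to no defined assessment.

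**2. Does anything else in the plan limit it?** The adherence check in section 3.6 tests enrolment against the criteria. An exclusion on judgement satisfies a criterion that permits judgement, so the check cannot flag it. The monitor's review covers screening records, but no section requires a reason for each exclusion or a count by site. The 20% validation set comes from the patients already enrolled, so it carries the same selection as the training set.

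**3. The plan's own figures.** Section 4.1 uses incidence 0.139, 24 parameters, shrinkage 0.9 and a Cox-Snell R² of 0.051: n = 24 / [(0.9 − 1) × ln(1 − 0.051/0.9)] = 4114.1, against 4115 stated, and 4115 × 0.139 = 572 events. These reproduce. The point does not rest on them; only the 13.9% incidence is carried forward.

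**4. Illustration by hand (assumed inputs).** Let a fraction f be excluded, with k times the risk of those kept. Incidence among those kept is 0.139 / (1 − f + fk), and the share of all cases excluded is fk / (1 − f + fk).
- f = 0.02, k = 2: 0.139/1.02 = 13.6%; 561 events in 4115; 4% of cases excluded.
- f = 0.10, k = 3: 0.139/1.20 = 11.6%; 477 events in 4115; 25% of cases excluded.

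**5. Effect on AUC (assumed inputs).** The model is a normal risk score with equal variance in cases and non-cases, separated by √2 × Φ⁻¹(AUC): 0.661 for AUC 0.68 and 0.954 for AUC 0.75. Prevalence is 0.139, with 4 million simulated patients. The documents give no AUC. In this model 0.68 implies a Cox-Snell R² of about 0.050, close to the planned 0.051; 0.75 is a more optimistic case. Investigator judgement correlates r with the score, and the patients judged worst are removed. Cells show AUC and incidence after exclusion; the third decimal of the AUC carries simulation error.

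| Starting AUC | Excluded | r = 0.3 | r = 0.5 | r = 1 (exact top of score) |
|---|---|---|---|---|
| 0.68 | 5% | 0.679; 13.6% | 0.676; 13.4% | 0.659; 12.7% |
| 0.68 | 10% | 0.678; 13.4% | 0.674; 13.0% | 0.647; 11.9% |
| 0.75 | 5% | 0.748; 13.5% | 0.745; 13.1% | 0.721; 12.1% |
| 0.75 | 10% | 0.747; 13.2% | 0.741; 12.6% | 0.704; 10.9% |

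With imperfect judgement the loss in AUC is about 0.001 to 0.009. With perfect judgement it is about 0.02 to 0.05. The calculation holds the score fixed, so it does not capture less stable coefficients in sparse predictor levels.

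**The case against.** The strongest reply is that this is template wording with little practical effect.

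- **Direction.** The clause speaks only of certain conditions and mentions neither frailty nor severity. Other parts of the plan point towards keeping severe cases: Table 1 deliberately collects them, and the first footnote to Table 2 allows consent after surgery in urgent situations. A site might equally use the clause for patients whose skin cannot be examined. This stands. A reader might infer that the frailest patients will be left out, or that this is intended; the documents support neither.
- **Size.** The larger losses in AUC arise only if investigators remove exactly the top of the risk score, which they cannot know before surgery. This stands too. Those figures are an upper bound.
- **Meaning.** Death, infection and complications are followed at scheduled visits, so the safety half of the clause could loosely be read as those outcomes. This softens the wording point but does not tell a site which conditions to exclude, and it leaves the efficacy half without an object.
- **Controls.** Section 3.6 provides for training, site visits, audits and review of screening records. These are real controls, but they neither define the clause nor require or report reasons.

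**Conclusion.** The point holds as a defect in an eligibility rule. The clause has no clear referent in this cohort, leaves exclusion to each site's judgement, and conflicts with the stated population of all surgical patients. It could remove high-risk patients whose severity levels are candidate predictors, and internal validation would not reveal that.

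How often the clause will be used, and on whom, cannot be derived from the documents. Under the assumed 5% to 10% exclusion and a starting AUC of 0.68 or 0.75, the likely loss in AUC is below 0.01. The upper bound is about 0.02 to 0.05, with incidence falling from 13.9% to 12.7% or 11.9% (AUC 0.68), or to 12.1% or 10.9% (AUC 0.75). It would go too far to say that the clause will materially bias the model. This is a cheap improvement, and no stated sample-size figure changes because of it.

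**What to change.** Delete the sentence in section 2.4. If the team wants a practical exclusion, replace it with named, objective reasons limited to inability to assess the predictors or the skin outcome, for example skin that cannot be inspected.

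In either case, state in section 3.6 that every screened patient excluded under such a reason is recorded with that reason, and plan to report the number and reasons by site in the participant flow. The screening records that the monitor already reviews can carry this.

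The cost is one edited sentence and a small logging burden at sites. It is best done before or early in enrolment, because exclusions that were not logged cannot be recovered later.
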